4.3 STUDY TREATMENT AND OTHER TREATMENTS RELEVANT TO THE STUDY DESIGN

The IMP for this study is entrectinib.

4.3.1 Study Treatment Formulation, Packaging, and Handling

The reference treatment in Part 1 and Part 2, Entrectinib (RXDX-101) F06 hard capsules, 200 mg (fine API) (Ro 710-2122/F04) will be provided by the Sponsor as capsules for oral administration.

In Part 1, two multi-particulate formulations will be investigated. The formulations will be manufactured, packaged, and provided by the Sponsor as 2.5 mg film-coated mini-tablets for oral administration. The formulation will be supplied as a 600-mg dose in a bottle.

In Part 2, the test formulation, Entrectinib F06 HPMC Capsules 200 mg (coarse API) for oral administration will be manufactured by Quotient Sciences.

For information on the formulation and handling of entrectinib, see the Investigational Medicinal Product Dossier (IMPD).

Entrectinib—Genentech, Inc.
29/Protocol GP41341, Version 1 – 02 April 2019

4.3.2 Study Treatment Dosage, Administration, and Compliance

The treatment regimens are summarized in Section 3.1.

Refer to the dosing instructions for detailed instructions on drug preparation, storage, and administration.

Any dose modification should be noted on the Study Drug Administration electronic Case Report Form (eCRF). Cases of accidental overdose or medication error, along with any associated adverse events, should be reported as described in Section 5.3.5.

Guidelines for treatment interruption or discontinuation for subjects who experience adverse events are provided in Section 4.6.

4.3.2.1 Entrectinib

In Part 1, each subject will be randomized to receive a single oral dose of 600 mg entrectinib in each of three treatment periods; the following formulations will be administered:

- Multi-particulate formulation 1: Entrectinib film-coated mini-tablets, 600 mg (240 × 2.5 mg) (Ro 710-2122/F15) (test formulation 1; T1)
- Multi-particulate formulation 2: Entrectinib film-coated mini-tablets, 600 mg (240 × 2.5 mg) (Ro 710-2122/F16) (test formulation 2; T2)
- F06 capsule formulation: Entrectinib (RXDX-101) F06 hard capsules, 600 mg (3 × 200 mg) (Ro 710-2122/F04) (reference formulation; R)

The test formulation will be mixed with approximately one tablespoon (~15 mL) of yoghurt which will be swallowed without chewing with approximately 240 mL of water. The reference formulation will be dosed as 3 × 200 mg capsules, swallowed whole with approximately 240 mL of water. Additional water may be given with the IMP if required.

In Part 2, each subject will be randomized to receive a single oral dose of 200 mg entrectinib under fasted conditions in each of two treatment periods; the following formulations will be administered:

- Entrectinib F06 HPMC capsules (coarse API), 200 mg (test formulation; T)
- Entrectinib (RXDX-101) F06 hard capsules, 200 mg (Ro 710-2122/F04) (fine API) (reference formulation; R)

The formulations will be dosed as 1 × 200 mg capsules, swallowed whole with approximately 240 mL of water after an overnight fast (minimum 8 hours).

4.3.3 Investigational Medicinal Product Accountability

Quotient Sciences will manufacture the Entrectinib F06 HPMC capsules (coarse API). The Entrectinib (RXDX-101) F06 hard capsules (fine API) (Ro 710-2122/F04) and the

Entrectinib—Genentech, Inc.
30/Protocol GP41341, Version 1 – 02 April 2019

multi-particulate formulations (Entrectinib film-coated mini-tablets), will be provided by the Sponsor.

The study site will acknowledge receipt of IMPs supplied by the Sponsor by returning the appropriate documentation form to confirm the shipment condition and content. Any damaged shipments will be replaced.

Investigational medicinal products (IMPs) will either be disposed of at the study site according to the study site's institutional standard operating procedure or be returned to the Sponsor with the appropriate documentation. The site's method of destroying Sponsor-supplied IMPs must be agreed to by the Sponsor. The site must obtain written authorization from the Sponsor before any Sponsor-supplied IMP is destroyed, and IMP destruction must be documented on the appropriate form.

Accurate records of all IMPs received at, dispensed from, returned to, and disposed of by the study site should be recorded on the Drug Inventory Log.

4.4 CONCOMITANT THERAPY, PROHIBITED FOOD, AND ADDITIONAL RESTRICTIONS

Concomitant therapy consists of any medication (e.g., prescription drugs, over-the-counter drugs, vaccines, topical medications, herbal or homeopathic remedies, nutritional supplements) used by a subject in addition to protocol-mandated treatment from screening until the Follow-up phone call (12 to 14 days after the last dose of study drug). All such medications should be reported to the investigator and recorded on the Concomitant Medications eCRF.

4.4.1 Permitted Therapy

Paracetamol up to 4 g per day, medications to treat adverse events, vitamins and minerals, hormonal contraceptives and hormone replacement therapy are allowed throughout the study. Other medications for chronic, non-clinically significant, conditions (e.g., thyroid hormone replacement medication) may be permitted providing the subject has been on a stable dose and dosing regimen for at least 3 months preceding screening.

If any medication is required, the name, strength, frequency of dosing and reason for its use will be documented in the subject's source data.

Entrectinib—Genentech, Inc.
31/Protocol GP41341, Version 1 – 02 April 2019

4.4.2 Prohibited Therapy

Subjects should not take any prescription or over-the-counter medication from 14 days prior to dosing until after the Follow-up phone call (12 to 14 days after the last dose of study drug) unless the investigator has given prior consent. The following categories of medication are specifically prohibited:

- Moderate or potent inhibitors or inducers of CYP3A enzymes or P-gp transporter.
- Gastric pH-modifying agents such as proton pump inhibitors, H2 receptor antagonists, and antacids.
- Psychoactive drugs or other drugs used for mental disorders. Examples include antidepressants, anti-psychotics, sedatives, and stimulants.

4.4.3 Prohibited Food

Subjects should refrain from eating food containing poppy seeds for 48 hours prior to screening and for 48 hours prior to admission until 96 hours post-dose in each period.

Subjects should not consume grapefruit, Seville oranges or food and beverages containing caffeine/xanthines during the study (from 24 hours prior to admission in Period 1 until 96 hours post-dose in each period).

Subjects will be required to refrain from smoking from 12 months prior to screening until 96 hours after the final dose of IMP, and abstain from consumption of alcohol during the 24 hours prior to screening and from admission to the clinic in Period 1 until 96 hours post-dose in each period.

4.4.4 Additional Restrictions

No food or fluids other than water will be allowed for 8 hours prior to each study visit until after study laboratory samples are obtained (see [Appendix 1](#)).

In Part 1, subjects will be provided with a light snack on the evening of Day -1 and will fast from all food and drink (except water) until the following morning, when they will be provided with a pediatric breakfast. The breakfast should be consumed over a maximum period of 25 minutes, with dosing occurring 30 minutes after the start of breakfast. Subjects should be encouraged to eat their meal evenly over the 25-minute period. It is acknowledged that some subjects will take less time to eat, but dosing should still occur 30 minutes after the start of breakfast.

In Part 2, subjects will be provided with a light snack on the evening of Day -1 and no food will be allowed until 4 hours after dosing and water will be permitted freely until 1 hour prior to and after 1 hour following dosing of entrectinib.

Lunch will be provided at approximately 4 h post-dose, an evening meal at approximately 10 h post-dose and an evening snack at approximately 14 h post-dose.

Entrectinib—Genentech, Inc.
32/Protocol GP41341, Version 1 – 02 April 2019

On subsequent days, meals will be provided at appropriate times. Meals will be similar among cohorts.

Subjects will be allowed water up to 1 hour before the scheduled dosing time and will be provided with 240 mL of water at 1 hour post dose. Water will be allowed ad libitum after 1 h post-dose. Decaffeinated fluids will be allowed ad libitum from lunch time on the day of dosing.

Subjects should refrain from strenuous exercise from 48 hours prior to admission to the clinic and during the period of confinement and will otherwise maintain their normal level of physical activity throughout the entire study (i.e., will not begin a new exercise program or participate in any unusually strenuous physical exertion).

4.5 STUDY ASSESSMENTS

The schedule of activities to be performed during the study is provided in [Appendix 1](#). All activities should be performed and documented for each subject.

There are times where the protocol requires more than one procedure to be completed at the same time point. In these instances, the following will apply to post-dose time points:

Pharmacokinetic samples should take priority over other procedures scheduled at the same time point.

Electrocardiograms should be taken prior to vital signs when both measurements are scheduled at the same time point. Other assessments, e.g., physical examinations etc., will be performed within the required time windows.

All safety assessments will be timed and performed relative to the start of dosing.

4.5.1 Informed Consent Forms and Screening Log

Written informed consent for participation in the study must be obtained before performing any study-related procedures (including screening evaluations). Informed Consent Forms for enrolled subjects and for subjects who are not subsequently enrolled will be maintained at the study site.

Subjects will be provided with a written explanation of the study at least the day before the screening visit. A physician or nurse will explain to each subject the nature of the study, its purpose, expected duration and the benefits and risks involved in study participation. Subjects will be informed that, for safety reasons, brief details of their involvement in the study may be revealed to other units and companies that carry out clinical studies in the local area. Subjects will then be given the opportunity to ask

Entrectinib—Genentech, Inc.
33/Protocol GP41341, Version 1 – 02 April 2019

questions and will be informed of their right to withdraw from the study without prejudice. After this explanation and before entering the study, the subject will voluntarily sign an ICF. Until written consent has been obtained from the subject, no study specific procedure or investigation will be performed. If an amendment is made to the participant information sheet, participants will be re-consented to the most current version of the ICF(s) where appropriate.

All screening evaluations must be completed and reviewed to confirm that subjects meet all eligibility criteria before enrollment. The investigator will maintain a screening log to record details of all subjects screened and to confirm eligibility or record reasons for screening failure, as applicable.

If the start of the study is delayed for any reason so that the interval between screening and first dose exceeds 28 days, all or part of the screening procedures may be repeated at the discretion of the investigator.

This study permits the re-screening of a subject who has discontinued the study as a pre-treatment failure (i.e., subject has not been randomized/has not been treated); the reason for failure must be temporary and expected to resolve. If re-screened, the subject must be re-consented.

4.5.2 Medical History, Concomitant Medication, and Demographic Data

Medical history, including clinically significant diseases, surgeries, cancer history (including prior cancer therapies and procedures), reproductive status, smoking history, and use of alcohol and drugs of abuse, will be recorded at baseline (screening). In addition, all medications (e.g., prescription drugs, over-the-counter drugs, vaccines, herbal or homeopathic remedies, nutritional supplements) used by the subject since screening will be recorded.

Demographic data will include age, sex, and self-reported race/ethnicity. Height and weight will be recorded at screening.

4.5.3 Physical Examinations

A complete physical examination, performed at screening, should include an evaluation of the head, eyes, ears, nose, and throat, and the cardiovascular, dermatologic, musculoskeletal, respiratory, gastrointestinal, and neurologic systems. Any abnormality identified at baseline (Period 1 admission) should be recorded on the General Medical History and Baseline Conditions eCRF.

Limited, symptom-directed physical examinations should be performed on Day -1, and as clinically indicated throughout the study. Changes from baseline abnormalities should be recorded in subject notes. New or worsened clinically significant abnormalities should be recorded as adverse events on the Adverse Event eCRF.

Entrectinib—Genentech, Inc.
34/Protocol GP41341, Version 1 – 02 April 2019

4.5.4 Vital Signs

Vital signs will include measurements of pulse rate, and systolic and diastolic blood pressure while the subject is in a supine position for 5 minutes, and oral temperature.

The acceptable deviations from the nominal vital signs measurement time points are:

- The pre-dose vital signs measurements will be taken ≤ 2 hours before dosing.
- Post-dose vital signs measurements will be taken ± 15 minutes from the nominal post-dose time points.
- Discharge vital signs measurements will be taken ± 1 hour from the nominal time point.
- For return visits vital signs measurements will be taken ± 4 hours from the nominal return visit time point.

Record abnormalities observed at baseline on the General Medical History and Baseline Conditions eCRF. At subsequent visits, record new or worsened clinically significant abnormalities on the Adverse Event eCRF. The Day 1, pre-dose assessment in each period will be used as baseline.

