5.3.1 Adverse Event Reporting Period

Investigators will seek information on adverse events at each subject contact. All adverse events, whether reported by the subject or noted by study personnel, will be recorded in the subject's medical record and on the Adverse Event eCRF.

After informed consent has been obtained but prior to initiation of study drug, only serious adverse events caused by a protocol-mandated intervention (e.g., invasive procedures such as biopsies, discontinuation of medications) should be reported (see Section [5.4.2](#) for instructions for reporting serious adverse events).

After initiation of study drug, all adverse events will be reported until the Follow-up phone call (12 to 14 days after the final dose of study drug).

Instructions for reporting adverse events that occur after the adverse event reporting period are provided in Section [5.6](#).

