5.3.5.5 Abnormal Vital Sign Values

Not every vital sign abnormality qualifies as an adverse event. A vital sign result must be reported as an adverse event if it meets any of the following criteria:

- Is accompanied by clinical symptoms
- Results in a change in study treatment (e.g., dosage modification, treatment interruption, or treatment discontinuation)
- Results in a medical intervention or a change in concomitant therapy
- Is clinically significant in the investigator's judgment

It is the investigator's responsibility to review all vital sign findings. Medical and scientific judgment should be exercised in deciding whether an isolated vital sign abnormality should be classified as an adverse event.

If a clinically significant vital sign abnormality is a sign of a disease or syndrome (e.g., high blood pressure), only the diagnosis (i.e., hypertension) should be recorded on the Adverse Event eCRF.

Observations of the same clinically significant vital sign abnormality from visit to visit should only be recorded once on the Adverse Event eCRF (see Section [5.3.5.3](#) for details on recording persistent adverse events).

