5.3.5.8 Preexisting Medical Conditions

A preexisting medical condition is one that is present at the screening visit for this study. Such conditions should be recorded on the General Medical History and Baseline Conditions eCRF.

A preexisting medical condition should be recorded as an adverse event only if the frequency, severity, or character of the condition worsens during the study. When recording such events on the Adverse Event eCRF, it is important to convey the concept that the preexisting condition has changed by including applicable descriptors (e.g., "more frequent headaches").

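### Protocol 4.5.4 uses one per-period baseline both for change scores and for choosing the recording form, so a vital-sign abnormality first seen before a later dose has two possible destinations

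*Protocol*

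**What the plan says.** Protocol 4.5.4 (Vital Signs) closes with three consecutive sentences:

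1. "Record abnormalities observed at baseline on the General Medical History and Baseline Conditions eCRF".
2. "At subsequent visits, record new or worsened clinically significant abnormalities on the Adverse Event eCRF".
3. "The Day 1, pre-dose assessment in each period will be used as baseline".

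Other sections bear on the same choice of form:

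- Protocol 4.5.3 (Physical Examinations) names the same history form but ties it to one time point: "Any abnormality identified at baseline (Period 1 admission) should be recorded on the General Medical History and Baseline Conditions eCRF".
- Protocol 5.3.1: "After initiation of study drug, all adverse events will be reported until the Follow-up phone call". Nothing resets this between periods.
- Protocol 5.3.5.5: "A vital sign result must be reported as an adverse event if it meets any of the following criteria". One criterion is clinical significance in the investigator's judgment. There is no exception for a later period's pre-dose reading.
- Protocol 5.3.5.8: "A preexisting medical condition is one that is present at the screening visit for this study".
- SAP 3.2.3 and 10.5.1 use a baseline specific to each period for vital-sign change scores. SAP 10.3 counts treatment-emergent events from the first dose of study drug and assigns washout events to the treatment given before that washout.

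**The concern.** In a crossover, a baseline specific to each period is a sensible reference for change scores. It is not a sensible boundary between medical history and adverse events, because from Period 2 onward the subject has already received study drug. Protocol 4.5.4 uses the same word for both purposes.

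A site that joins the first and third sentences would enter an abnormality first seen at a Period 2 or 3 pre-dose reading on the history form. If it were entered only there, it would not reach the treatment-emergent event tables, since SAP 7.6 only lists medical history. It would not count as a substantial change under SAP 10.5.1 either, because that reading is itself the reference value.

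Adverse event incidence is a secondary endpoint (Protocol 2.2). Any such error would run one way, towards fewer events for the preceding formulation.

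**Working it through.** The point rests on wording, so the check follows a vital-sign abnormality through the protocol according to when it is first observed.

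- **Period 1, Day 1 pre-dose.** The first sentence of 4.5.4 sends it to the history form. The screening anchor in 5.3.5.8 is narrower. But before dosing, 5.3.1 asks only for serious events caused by a protocol procedure, so no post-exposure event is lost.
- **Any post-dose reading (2, 6, 48 or 96 h in the SAP's mock vital-signs table).** The second sentence of 4.5.4 sends a new or worsened clinically significant finding to the adverse event form. There is no conflict.
- **Period 2 or 3, Day 1 pre-dose.** The first and third sentences together send it to the history form. The second sentence can be read the other way, since this visit comes after the Period 1 baseline. Sections 5.3.1 and 5.3.5.5 require an adverse event entry if the finding qualifies. By 5.3.5.8 it is not a pre-existing condition if it was absent at screening, and by 4.5.3 the history form closes at Period 1 admission. This is the only case with two destinations.

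The second sentence does not fully settle the third case. With a baseline in every period, a subsequent visit can mean one after that period's baseline, and worsening can be judged against that baseline. Protocol 4.5.6 uses the same per-period baseline for ECGs but attaches no history-form instruction to it. Of the three assessment sections, only 4.5.4 combines the two, which looks like a drafting slip.

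These readings matter because the schedule places no vital signs on Day -1 and follow-up is a telephone call. A later period's pre-dose reading is therefore the only scheduled vital-sign measurement between 96 h and the next dose.

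Readings exposed to the ambiguity, from the planned enrolment of 15 in Part 1 (three periods) and 16 in Part 2 (two periods), assuming everyone completes:

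- All Day 1 pre-dose readings: 15 × 3 + 16 × 2 = 45 + 32 = 77.
- Those after an earlier dose: 15 × 2 + 16 × 1 = 30 + 16 = 46.
- By preceding formulation: in Part 1 each formulation is given to 5 subjects in each period, so 5 × 2 = 10 of its 15 doses are followed by a later pre-dose reading (3 × 10 = 30). In Part 2 it is 8 of 16 (2 × 8 = 16). The exposure is balanced across formulations.

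Most that one misfiled event could change a formulation's incidence: 1/15 = 6.7 percentage points in Part 1, or 1/16 = 6.3 in Part 2. This is a ceiling. SAP 10.3.1 counts a subject once per treatment, so overall incidence moves only if that subject had no other event on that treatment.

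**The case against.** The strongest reply is that the protocol read as a whole already gives the right answer. The sentence on subsequent visits stands in the same paragraph, and 5.3.5.5, the section specific to vital signs, makes a qualifying result a mandatory adverse event. Nor does 4.5.4 say that a history entry replaces an adverse event entry. A careful investigator would file correctly, and site training on the eCRF (Protocol 7.2), which is not in the documents, may already deal with it. All of this stands, and it is why the point is minor. It does not remove the contradictory instruction.

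Three stronger readings are tempting, and the documents do not support them.

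- A reader might infer that any abnormality arising after Period 1 dosing can be filed as history. Those seen at post-dose readings go to the adverse event form under 4.5.4 itself. Nor is every new abnormality reportable: 5.3.5.5 says that not all of them qualify.
- A reader might infer that the vital-sign endpoint loses data. SAP 10.5.1 and 10.5.2 summarise and list the values whichever form is used, flag those outside the reference range, and list the out-of-range values separately.
- A reader might infer that a worsened state becomes the new normal for the next formulation because of this rule. That follows from the per-period analysis baseline, which is appropriate for change scores and should be kept.

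The affected findings are also likely to be few. They must be first seen at about 14 days or more after the previous dose. With the stated half-life of 20 to 30 hours, 336 h is 336/30 = 11 to 336/20 = 17 half-lives.

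**Conclusion.** The inconsistency is real, and its severity is minor. It is confined to vital-sign abnormalities first observed at the Day 1 pre-dose reading of Period 2 or 3. For those, 4.5.4 can be read as directing a post-exposure finding to the history form, against 4.5.3, 5.3.1, 5.3.5.5 and 5.3.5.8. Any resulting error can only reduce adverse event counts, for the formulation given in the preceding period.

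The 46 of 77 readings show how often the question could arise, and 6.7 or 6.3 points is the most a single event could matter. Neither is an expected effect. The documents give no rate of such findings and do not include the form-completion instructions, so no expected number of misfilings can be derived. The pharmacokinetic endpoints, sample size and error rates are untouched.

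**What to change.** Reconcile 4.5.4 with 4.5.3, 5.3.1 and 5.3.5.5. State that:

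- only abnormalities observed before the first dose in Period 1 go on the General Medical History and Baseline Conditions eCRF;
- from the first dose onward, including Day 1 pre-dose of later periods, new or worsened abnormalities that meet 5.3.5.5 go on the Adverse Event eCRF;
- the per-period pre-dose baseline applies to change-from-baseline summaries only.

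The cost is a short wording change in the protocol and in any eCRF completion instruction that repeats it. No visit, measurement or analysis is added, and SAP 3.2.3, 10.3 and 10.5.1 can stay as they are.
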